**PROTOCOL SYNOPSIS**

STUDY TITLE:	A Randomised, Double-Blind, Placebo-Controlled, Phase II Study to Assess the Efficacy and Safety of Orally Administered DS102 in Patients with Severe Acute Decompensated Alcoholic Hepatitis.
SHORT TITLE:	Efficacy and Safety of Orally Administered DS102 in Patients with Severe Acute Decompensated Alcoholic Hepatitis.
PHASE:	II
STUDY DURATION:	90 days (treatment duration: 28 days)
INVESTIGATIONAL PRODUCT:	DS102 Capsule Placebo (paraffin oil)
OBJECTIVES:	
Efficacy Objective:
 
 
• To compare the efficacy of orally administered DS102 capsules versus placebo, in the treatment of adult patients with severe acute decompensated Alcoholic Hepatitis (AH).
 
 
Safety Objective:
 
 
• To compare the safety of orally administered DS102 capsules versus placebo, in the treatment of adult patients with severe acute decompensated AH.
 
 
Pharmacokinetic Objective:
 
 
• To evaluate the pharmacokinetics (PK) of 15(S)-HEPE following orally administered DS102 capsules, in six adult patients with AH in the initial pilot phase of the study, followed by trough level assessment of 15(S)-HEPE in all study participants.
 

ENDPOINTS:	
Primary Endpoint
 
 
• % Change in MELD score from baseline to Day 28
 
 
Secondary Endpoints
 
 
• Change in total bilirubin from baseline to Day 7, 14, 21 and 28
 
• Proportion of patients showing a 25% reduction of bilirubin at day 7, 14, 21, and 28.
 
• Change in serum cytokeratin 18-M30/M65 from baseline to Day 7, 14, 21 and 28
 
• Change in AST levels from Baseline to Day 7, 14, 21 and 28
 
• Change in AST:ALT ratio from Baseline to Day 7, 14, 21, 28
 
• Change in MDF score from baseline to Day 7, 14, 21 and 28.
 
• Proportion of patients showing a 25% reduction in MELD score from baseline to Day 7, 14, 21 and 28
 
• Change in MELD score from baseline to Day 7, 14 and 21
 
• Change in modified Sequential Organ Failure Assessment (m-SOFA) from baseline to Day 7, 14, 21 and 28
 
• Proportion of patients with a 2-point worsening of m-SOFA
 

	
from baseline to Day 7, 14, 21 and 28.
 
 
• Change in hepatic encephalopathy as assessed by West Haven criteria, from baseline at Day 7, 14, 21 and 28
 
• Incidence of acute kidney injury over 28 days (defined by requiring medicinal or mechanical support)
 
• Incidence of variceal haemorrhage, ascites or hepatic encephalopathy over 28 days
 
 
Exploratory Endpoints
 
 
• Survival at day 7, 14, 21, 28 and 90 using Kaplan-Meier Plot
 
• Change in Gamma Glutamyl Transferase (GT) from Baseline to Day 7, 14, 21 and 28
 
• Change in ALT from Baseline to Day 7, 14, 21 and 28.
 
• Change in Child Pugh score from baseline to Day 7, 14, 21 and 28
 
• Change in APACHE-II score from baseline to Day 7, 14 and 28
 
• Change in Lille score from baseline to Day 7, 14 and 28
 
 
Safety Endpoints
 
 
• Treatment emergent (S)AE and SUSARs
 

STUDY DESIGN:	This is a multicentre, double blind, placebo controlled, 2-arm parallel group comparison (Phase 2) study, preceded by an open label pilot phase, in which six patients will receive open label treatment with DS102 1000mg twice daily within 30 minutes after a meal for 28 days. After the pilot phase, all patients will either receive 2000mg DS102 (1000mg BD) or placebo (BD), in addition to standard of care therapy, within 30 minutes after a meal for 28 days in the two treatment groups of 60 patients each. Before randomisation each patient will undergo a screening period of up to five days after signing informed consent.
TOTAL NUMBER OF RANDOMISED PATIENTS:	Approximately 126 male or female patients, aged 18 years or older, with evident severe acute decompensated AH will be included in this study.
STUDY POPULATION:	
INCLUSION CRITERIA:	
 
1. Male or female patients aged 18 years and older
 
2. Total bilirubin of <math>\geq 5</math> mg/dl (85<math>\mu</math>mol/l)
 
3. Patients with definite or probable AH
 
4. MELD <math>\geq 18</math> at baseline visit
 
5. Maddrey DF <math>\geq 32</math> at baseline visit
 
6. Aspartate aminotransferase (AST) <math>> 50</math> U/L
 
7. Aspartate aminotransferase/alanine aminotransferase (AST:ALT) ratio <math>> 1.5</math>
 

	
8. Female patients, or female partners of male patients, of child bearing potential must use highly effective birth control methods or have a sterilised partner for the duration of the study. Highly effective birth control methods are defined as methods that can achieve a failure rate of less than 1% per year when used consistently and correctly. Such methods include intrauterine device or sexual abstinence.
 
Note: A woman is considered of child bearing potential (WOCBP), i.e. fertile, following menarche and until becoming post-menopausal unless permanently sterile. Permanent sterilisation methods include hysterectomy, bilateral salpingectomy and bilateral oophorectomy.
 
Note: Hormonal contraceptives are contraindicated in patients with severe hepatic diseases and are not acceptable as a birth control method in this study.
 
Note: Sexual abstinence is considered a highly effective method only if defined as refraining from heterosexual intercourse during the entire period of risk associated with the study treatments. The reliability of sexual abstinence needs to be evaluated in relation to the duration of the clinical trial and the preferred and usual lifestyle of the subject
 
9. Patient and/or legally authorised representative must provide Informed consent
 
10. Able to swallow the provided study medication
 
11. Not eligible for liver transplant during this hospitalisation

--	--

EXCLUSION CRITERIA:	
 
1. Pregnant or lactating females.
 
2. Spontaneous liver function improvement defined by decrease of bilirubin level and MDF of >10% within 5 days of hospital admission
 
3. Grade 4 hepatic encephalopathy (West Haven Criteria)
 
4. Type 1 hepatorenal syndrome (HRS) or a serum creatinine >2 x ULN or requirement for haemodialysis
 
5. History of hypersensitivity to any substance in DS102 capsules or placebo capsules.
 
6. Alcohol abstinence of >6 weeks prior to screening
 
7. Duration of clinically apparent jaundice >3 months prior to baseline
 
8. Other causes of liver disease including:           
 
a. Evidence of chronic viral hepatitis (Hepatitis B DNA positive or HCV RNA positive)
 
b. Biliary obstruction
 
c. Hepatocellular carcinoma
 
d. Wilsons disease
 
e. Budd Chiari Syndrome
 
f. Non-alcoholic fatty liver disease
 
 
 
9. History of or active non-liver malignancies other than curatively treated skin cancer (basal cell or squamous cell carcinomas).
 
10. Previous entry into the study
 
11. AST >400 U/L or ALT >270 U/L
 
12. Treatment with any experimental drug within 30 days prior to Day 0 visit (Baseline), or 5 half-lives (whichever is longer).
 
13. Patients who have used dietary supplements rich in omega-3 or omega-6 fatty acids in the four weeks prior to baseline
 
14. Patients dependent on inotropic support (adrenaline or noradrenaline), including Terlipressin
 
15. Active variceal haemorrhage on this admission requiring more than 2 units of blood to maintain hemoglobin level within 48 h
 
16. Untreated or unresolved sepsis
 
17. Presence of refractory ascites
 
18. Patients with known cerebral haemorrhage, extensive retinal haemorrhage, acute myocardial infarction (within last 6 weeks)
 

----------------------------	--

	
or severe cardiac arrhythmias (not including atrial fibrillation)
 
19. Known infection with HIV at screening
 
20. Significant systemic or major illnesses other than liver disease that, in the opinion of the investigator, would preclude or interfere with treatment with DS102 and/or adequate follow up
 
21. Previous liver transplantation

CONCOMITANT MEDICATION	Patients requiring the need for treatment due to a comorbidity during the trial will be treated using the standards of care for that indication e.g. diabetes, cholesterol, infection management, etc.
TEST PRODUCT, DOSE, AND MODE OF ADMINISTRATION:	
DS102 will be provided in a capsule, containing 500mg of 15(S)-HEPE EE with 5% w/w of colloidal silicon dioxide as viscosity modifier.
 
Placebo (liquid paraffin) will be provided in a capsule containing equivalent fill weight of liquid paraffin. In the open label pilot phase 2000mg (1000mg BD) will be orally administered within 30 minutes after a meal for 28 days.
 
In the double-blind phase of the study either 2000mg (1000mg BD) or placebo (BD) will be orally administered, in addition to standard of care therapy, within 30 minutes after a meal for 28 days.

SAFETY	A Data and Safety Monitoring Board (DSMB) will be established and will meet regularly to monitor on-going safety.
EVALUATION CRITERIA:	
Efficacy:
 
 
• Total bilirubin
 
• MELD
 
• MDF
 
• Cytokeratin (CK) 18-M30/M65
 
• m-SOFA
 
• APACHE-II
 
• ALT
 
• AST
 
• AST:ALT ratio
 
• Gamma GT
 
• Child Pugh Score
 
• West Haven score (hepatic encephalopathy)
 
• Lille score
 
 
Safety:
 
 
• Physical examination, including height and weight
 
• ECG (6-lead or 12-lead)
 
• Vital signs, including blood pressure (BP), pulse and temperature
 
• Clinical laboratory tests (haematology, coagulation, biochemistry, plasma caeruloplasmin and virology)
 

	
 
• Pregnancy test for females of child bearing potential
 
• Adverse events (AEs)
 
• Concomitant medications
 
 
Pharmacokinetic:
 
Pilot Phase:
 
 
• <math>C_{max}</math> – maximum observed concentration
 
• <math>T_{max}</math> - time of maximum observed concentration
 
• <math>AUC_t</math> – Area under the concentration-time curve to time t
 
• <math>AUC_{tau}</math> - Area under the concentration-time curve to the end of the dosage interval
 
• <math>AUC_{inf}</math> - Area under the concentration-time curve extrapolated to infinite time
 
• %Extrapol – Percentage of <math>AUC_{inf}</math> obtained by extrapolation
 
• <math>K_{el}</math> – Apparent first-order terminal elimination rate constant
 
• <math>T_{1/2}</math> – Apparent first-order terminal elimination half-life
 
• <math>Flucp</math> – Fluctuation at pharmacokinetic steady-state
 
• <math>R_{ac}</math> – Accumulation ratio at pharmacokinetic steady-state
 
• <math>T_{ss}</math> – Time to achieve pharmacokinetic steady-state
 
 
Double-Blind Phase:
 
 
• <math>R_{ac}</math> – Accumulation ratio at pharmacokinetic steady-state
 
• <math>T_{ss}</math> – Time to achieve pharmacokinetic steady-state
 

EXPLORATORY	Blood samples will be collected at Baseline/Visit 2, Day 14/Visit 6 and Day 28/Visit 8 for the potential analysis of Severe Alcoholic Hepatitis biomarkers
STATISTICS	See Chapter 12
SPONSOR:	Afimmune Ltd

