## 7 PATIENTS AND SCREENING

In order to participate in this study the patients must meet all inclusion criteria and must not meet any of the exclusion criteria. Inclusion in the trial starts with the informed consent signature. The inclusion and exclusion criteria are to be verified at the screening visit (Visit 1) and at the start of treatment/baseline visit (Visit 2). Patient history of alcohol abuse for at least six months must be documented at enrolment.

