**Table 1: Child-Pugh Score (Jackson & Gleeson 2010)**

Factor	1 point	2 points	3 points
Bilirubin ( $\mu\text{mol litre}^{-1}$ )	< 34	34–50	< 50
Albumin (g litre $^{-1}$ )	> 35	28 – 35	< 28
INR	< 1.7	1.7 – 2.2	> 2.2
Ascites	None	Controlled	Refractory
Hepatic encephalopathy	None	I – II or controlled	III – IV or refractory

Blood samples will be taken to assess the Child-Pugh score at Visit 2/Baseline, Visit 3/Day 3, Visit 4/Day 5, Visit 5/Day 7, Visit 6/Day 14, Visit 7/Day 21, Visit 8/Day 28/Early Termination and Visit 9/Day 90/Follow up.

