6.3 General Derivations

- Definition of baseline

Baseline is defined as the last non-missing value (including scheduled and unscheduled assessments) prior to the patient receiving study treatment.

- Incomplete dates

For calculation purposes, incomplete dates will be completed using worst case. Further details are detailed in the relevant sections as required.

- Non-numeric values recorded in a numeric field

In the case where a variable is recorded as “>x”, “ $\geq x$ ”, “ $<x$ ” or “ $\leq x$ ” in a numeric field, then for analysis purposes a value of x will be taken. Where a range of values is quoted the midpoint of the range will be taken. For example, if a laboratory safety parameter is reported as being below the limit of quantification or $< x$, the value of the limit will be used in the calculation of summary statistics. The recorded value will be reported in listings.

- Methods for handling withdrawals and missing data

Imputation of any data will be detailed in the relevant sections.

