6.13.3.2 Descriptive summaries and listing

Covered under section [16.7](#).

6.13.4 Change in Child-Pugh score from baseline to day 7, 14, 21 and 28

The Child-Pugh score is a means of assessing the severity of chronic liver disease, including cirrhosis, based on five clinical parameters (bilirubin, albumin, INR, ascites and hepatic encephalopathy) scored on a scale of 1 to 3. A total score is which indicates the severity and prognosis of chronic liver disease is then derived.

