6.13.4.1 Analysis

Change in Child-Pugh score from baseline up to and including day 28 will be assessed with an MMRM analysis, using the FAS, including terms for treatment group, visit, treatment-by-visit as fixed effects and the baseline Child-Pugh score as a covariate.

The adjusted treatment means and adjusted mean difference between the active dose and placebo will be presented along with 95% CI and p-value for the day 7, 14, 21 and 28 timepoint.

The modelling process described in section 6.11.1 will be followed.

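### The Child-Pugh table in Protocol 9.1.5 prints its 3-point bilirubin band as `< 50` µmol/l, apparently a reversed sign, so the item cannot be scored as printed for any eligible patient at baseline

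*Protocol*

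**What the plan says.** The Child-Pugh table in Protocol 9.1.5 has five rows, each scored 1, 2 or 3 points. The bilirubin row, in µmol/l, reads `< 34`, `34–50` and `< 50`. The INR row reads "< 1.7 1.7 – 2.2 > 2.2", and the albumin row reads `> 35`, `28 – 35` and `< 28`.

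Inclusion criterion 2 (Synopsis and Protocol 7.2) requires "Total bilirubin of \geq 5 mg/dl (85 \mu mol/l"). Protocol 7 adds: "The inclusion and exclusion criteria are to be verified at the screening visit (Visit 1) and at the start of treatment/baseline visit". SAP 6.3 states: "Baseline is defined as the last non-missing value (including scheduled and unscheduled assessments) prior to the patient receiving study treatment".

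The score feeds one exploratory endpoint: "Change in Child Pugh score from baseline to Day 7, 14, 21 and 28". SAP 6.13.4 describes it as "based on five clinical parameters (bilirubin, albumin, INR, ascites and hepatic encephalopathy) scored on a scale of 1 to 3", with a total then derived, but gives no cut-offs. SAP 6.13.4.1 analyses the change by MMRM with "the baseline Child-Pugh score as a covariate". The list of changes from the protocol in SAP 6.25 does not mention the table.

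**The concern.** The bilirubin row contradicts itself. Its worst band contains the whole of the best band and nearly all of the middle one, and it leaves everything above 50 µmol/l without a score. In this trial that is the range in which every eligible patient starts.

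Both the change from baseline and the baseline covariate in the MMRM need a baseline Child-Pugh total, and the total needs a bilirubin item. The table is the only scoring rule in either document. If it were applied as printed at data entry or in programming, the baseline item would be undefined, and a patient whose bilirubin falls could be given either a better score or the worst one. SAP 2.3 plans 50 sites in 9 countries, so the ambiguity could be settled differently in different places.

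**Working it through.** The plan gives no calculated figure to reproduce here. The check applies the printed bands to bilirubin values, then repeats this with the 3-point sign reversed.

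**Inputs**
- Bands in µmol/l: 1 point `< 34`; 2 points `34–50`; 3 points `< 50` (Protocol 9.1.5).
- Entry threshold: 85 µmol/l (inclusion criterion 2, which states the value in both units, so no conversion is needed).
- Total: five items, each 1 to 3 points, so 5 × 1 = 5 up to 5 × 3 = 15.

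**Step 1. Direction of the signs**

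| Row | 1 point | 3 points | Sign turns round? |
|---|---|---|---|
| Albumin | `> 35` | `< 28` | yes |
| INR | `< 1.7` | `> 2.2` | yes |
| Bilirubin | `< 34` | `< 50` | no |

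Bilirubin is the only numeric row that breaks the pattern.

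**Step 2. Points that each value satisfies**

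| Bilirubin (µmol/l) | As printed | With 3 points at `> 50` |
|---|---|---|
| 20 | 1 and 3 | 1 |
| 33.9 | 1 and 3 | 1 |
| 34 | 2 and 3 | 2 |
| 49.9 | 2 and 3 | 2 |
| 50 | 2 | 2 |
| 50.1 | none | 3 |
| 76.5 | none | 3 |
| 85 | none | 3 |
| 300 | none | 3 |

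**Step 3. Baseline.** Because 85 > 50, every eligible value lies in the gap. On a grid from 85 to 1000 µmol/l in steps of 0.1, 0 of 9151 values fall in any printed band; with the sign reversed, all 9151 score 3. The result does not depend on the exact timing of the baseline sample. A 10% fall from 85 gives 0.90 × 85 = 76.5, still in the gap. Leaving the gap needs a fall to 50, which is 1 − 50/85 = 41.2%.

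**Step 4. After improvement.** Under the reversed sign, a fall from 85 to below 34 (more than 1 − 34/85 = 60%) moves the item from 3 to 1. The printed row also permits 3, a discrepancy of 3 − 1 = 2 points. For a value from 34 to just under 50, the discrepancy is 3 − 2 = 1 point.

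**Step 5. Reach.** MELD is calculated from variables that include INR, creatinine and bilirubin (Protocol 9.1.1). The two bilirubin secondary endpoints use bilirubin itself (SAP 6.12.1 and 6.12.2). Encephalopathy incidence uses a different Child-Pugh item (SAP 6.12.13). The eligibility criteria, the sample size (Protocol 12.3), the stopping criteria (7.8) and the liver-injury criteria (11.3.1) do not use the Child-Pugh score.

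**The case against.** The strongest reply is that nobody would score from this row literally. The columns run from best to worst, the intended order is evident, and staff who know the score will use the intended bands. The documents do not show the eCRF. SAP 6.12.13 refers to encephalopathy item scores of 1, 2 or 3 in the collected Child-Pugh data, which suggests that items reach the analysis already scored. The SAP does not say that the statistician applies the protocol's cut-offs. In addition, one sign in a machine-read table may be a reading error, although the albumin and INR signs in the same table came through coherently.

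Much of this stands. A reader might infer that no patient will have a usable Child-Pugh baseline, or that recovered patients will be scored as worst. The documents support neither. The first depends on eCRF bands that are not shown. As to the second, a recovered value meets two bands at once, so the rule is ambiguous rather than systematically worst. A reader might also take a bilirubin fall to be the drug's main expected effect; the documents do not say so, and the risk-benefit section names ALT and fibrosis.

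Blinding also limits the harm. A common misscoring rule applied to both arms would not create a difference where there is none, though it could blur a real one.

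What the reply does not do is supply a correct rule. Neither document contains one.

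**Conclusion.** The point holds as a minor error in a scoring rule. The fault is in the bilirubin row of the table in Protocol 9.1.5. Inclusion criterion 2 is not wrong; it explains why the fault covers every eligible patient at baseline. Taken literally, the item has no score at baseline and is ambiguous by 1 or 2 points once bilirubin falls below 50 µmol/l. Two points is a maximum: with the sign reversed, a patient who stays above 50 scores 3 throughout, and the documents do not allow an estimate of how many would fall to 50 or lower.

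The conclusion rests on two assumptions: that the sign is printed this way in the original, and that `> 50` is what was intended. The second is the simplest reading that removes both the overlap and the gap, and it matches the other numeric rows; the cited source was not available to confirm it. The effect is confined to one item of one exploratory endpoint.

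**What to change.** 1. Confirm the sign against the original protocol page and the source that the table cites.
2. Change the 3-point bilirubin band in Protocol 9.1.5 to `> 50` µmol/l.
3. Before database lock, check the eCRF item scoring, or any programmed derivation, against the corrected band, and query any items already scored differently.
4. Have SAP 6.13.4 cite the corrected table and state whether items are scored at site or derived from laboratory values.

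The cost is one character in the protocol, one sentence in the SAP and one eCRF check. The protocol change still goes through the amendment procedure in Protocol 13.1. It could reasonably be treated as non-substantial, but that classification is for the sponsor to make.

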## LIST OF ABBREVIATIONS

15(S)-HEPE EE	15(S)-Hydroxy-Eicosapentaenoic Acid Ethyl Ester
AH	Alcoholic Hepatitis
ASH	Alcoholic Steatohepatitis
AE	Adverse Event
ALT	Alanine Aminotransferase
AST	Aspartate Aminotransferase
BMI	Body Mass Index
BP	Blood Pressure
BUN	Blood Urea Nitrogen
CAP	Controlled Attenuation Parameter
CK	Cytokeratin
COPD	Chronic Obstructive Pulmonary Disease
CRA	Clinical Research Associate
CRF	Case Report Form
CTA	Clinical Trial Agreement
CTCAE	Common Terminology Criteria for Adverse Events
EC	Ethics Committee
ECG	Electrocardiogram
eCRF	Electronic Case Report Form
EDC	Electronic Data Capture
ELF	Enhanced Liver Fibrosis Score
EPA	Eicosapentanoic Acid
Gamma GT	Gamma Glutamyl Transferase
GCP	Good Clinical Practice
GLP	Good Laboratory Practice
GMP	Good Manufacturing Practice
HIV	Human Immunodeficiency Virus
ICF	Informed Consent Form
ICH	International Conference on Harmonisation
IL-	Interleukin-
IPF	Idiopathic Pulmonary Fibrosis
INR	International Normalised Ratio
ISF	Investigator Site File
LC-MS/MS	Liquid Chromatography Tandem Mass Spectrometry
LPS	Lipopolysaccharide
LSLV	Last Subject Last Visit
MCP-1	Monocyte Chemoattractant Protein-1
MDF	Maddrey's Discriminant Function
MedDRA	Medical Dictionary for Regulatory Activities

MELD	Model End-stage Liver Disease
MHRA	Medicines and Healthcare products Regulatory Agency
m-SOFA	Modified Sequential Organ Failure Assessment
NAFLD	Non-Alcoholic Fatty Liver Disease
NAS	NAFLD Activity Score
NASH	Non-Alcoholic Steatohepatitis
NFS	NAFLD Fibrosis Score
NOAEL	No Observed Adverse Effect Levels
OTC	Over the Counter
PBMC	Peripheral Blood Mononuclear Cell
PI	Principal Investigator
PIS	Patient Information Sheet
PK	Pharmacokinetic
PV CRO	Pharmacovigilance Contract Research Organisation
SAE	Serious Adverse Event
SAP	Statistical Analysis Plan
SDV	Source Data Verification
SIRS	Systemic Inflammatory Response Syndrome
SMC	Safety Monitoring Committee
SOP	Standard Operating Procedure
SUSAR	Suspected Unexpected Serious Adverse Reaction
TGF- $\beta$	Transforming Growth Factor – Beta
TNF- $\alpha$	Tumour Necrosis Factor – Alpha
WOCBP	Women of Child Bearing Potential

## 1 INTRODUCTION

### 1.1 Therapeutic Area and Disease Background

Alcoholic hepatitis (AH) is a clinical condition characterised by jaundice accompanied by elevated levels of serum aspartate transaminase (AST). Excessive alcohol consumption is a precursor to the condition (Crabb et al. 2016). AH is a major cause of hospitalisation due to liver-related conditions in those with a history of heavy alcohol intake, also a condition prominently associated with repeated hospitalisations (Sanyal & Gao. 2015). Excessive consumption of alcohol is the third leading preventable cause of death in the United States. Regular alcohol consumption can lead to hepatic steatosis, which eventually progresses to steatohepatitis, fibrosis and cirrhosis. In up to 40% of patients, severe acute alcoholic hepatitis has a mortality rate of six months (Lavallard et al. 2011). AH or alcoholic steatohepatitis (ASH) as its histological equivalent occurs in up to 35% of excessive alcohol consumers and is often a precursor of cirrhosis (Menachery & Duseja 2011). However, the severe acute form of AH - as evaluated in this study - is a rare, acute liver disease characterised by self-sustained inflammation of the liver, often leading to multi organ failure with a mortality exceeding 30% (Mark Thursz et al, STOPAH Trial, 2015)

AH is diagnosed by patient history and anamnesis, observation of rapid onset of high bilirubin values, AST>ALT (and both <500) and may be histologically confirmed by liver biopsy (ASH). The condition is always accompanied by different degrees of fibrosis of the liver. Severe acute decompensated AH may also include such hallmarks as macrovesicular steatosis together with neutrophil infiltration, hepatocyte injury and Mallory-Denk bodies. The presence of megamitochondria, satellitosis and cholestasis is also often observed (Crabb et al. 2016). If left untreated, severe acute decompensated AH can progress to multiorgan failure, sepsis and death.

